patients - across sites - receiving nodal radiotherapy out of any radiotherapy	P1 = Total number of patients 404684003 Clinical finding (finding) WITH 108290001 Radiotherapy (procedure)
	P2 = Total number of patients 404684003 Clinical finding (finding) WITH 168522007 Radiotherapy for lymphatic irradiation (procedure)

The actual metrics/ endpoints can then be defined as follows.

Objective	(Secondary) end point	
Metric 1. Time required to compute different queries of interest within the BC registry	Metric definition: Time to have an answer to the 3 queries (BC1, BC2 and BC3) with information from the BC registry - across sites Note 1: should include time of the BC specialist and supporting team (spending most of the time) Note2: should be the same between G1 and G2)	
	 Measurement: TBCx. User entry in dedicated "Data User form" (RedCap) for each of the queries 	
Metric 2: Accuracy of measurement	Metric definition: accuracy of the answer for each of the parameter between AIDAVA and the BC specialist	
	 Measurement: For each of the query (BC1, BC2, BC3), HBCx. Ask the value from the human (through RedCap Form) ABCx: get the value computed by AIDAVA ACCx: accuracy of calculation by AIDAVA (ABCx) compared to BC specialist (HBCx) 	

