SDPO	GO	With ± 15 patients on site	 EBCx: estimated total effort (person min, person hours or person days) for BC specialist and supporting local team to answer the queries (BC1, BC2, BC3 described in Section 3.2.1) across sites TBCx: estimated duration (min, hours or days) for the BC specialist to have an answer to the queries (BC1, BC2, BC3) across sites. Duration = time between the first request and the time the answer is provider 		
SDP1	G1	All patients	 EBCx: total effort for BC specialist (and local team) to answer the queries (BC1, BC2, BC3) across sites TBCx: duration (min, hours or days) for the BC specialist to have an answer to the queries (BC1, BC2, BC3) across sites. HBCx: answer to the query as provided by human BC specialist ABCx: answer to the query as computed by AIDAVA ACCx: accuracy of calculation by AIDAVA compared to BC specialist 		
SDP2	G2		Same than SDP1 - for G2		
		1	CVD		
SDP1	G1	All patients	 CVD. SMART risk score computed by AIDAVA TCVD1.1/TCVD1.2. Time required for the treating/ senior physician to compute the SMART score (collect + analyse + enter data into a standalone web page calculator) CVD1.1/CVD1.2. SMART score computed by treating / senior physician ACVD1.1/ACVD1.2. Accuracy of automatic calculation of the score compared to treating/senior physician-entered score 		
SDP2	G2		Same than SDP1 - for G2		

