A1	Sum across patient arms for G1 A1.M1 = M1@PDP4 + M1@PDP6 A1.M2.x = M2.x@PDP4 + M2.x@PDP6 A1.M3.x = M3.x@PDP4 + M3.x@PDP6 A1.M4.x = M4.x@PDP4 + M4.x@PDP6	Descriptive Statistics Performance in G1 of the AIDAVA system.			
A2	Sum across patient arms for G2	Descriptive Statistics			

Computed	Description of measures	Test & meaning (per H1)
	A2.M1 = M1@PDP5 + M1@PDP7 A2.M2.x = M2.x@PDP5 + M2.x@PDP7 A2.M3.x = M3.x@PDP5 + M3.x@PDP7 A2.M4.x = M4.1@PDP5 + M4.x@PDP7	Performance in G2 of the AIDAVA system.
A3	Difference in A1 and A2 (i.e. difference between G1 and G2 across all patients)	Unpaired t-test
	Α3.Μ1-Δ = Α1.Μ1 - Α2.Μ1	H1: G2 more usable than G1
	A3.M2.xΔ = A1.M2.x - A2.M2.x A3.M3.x-Δ = A1.M3.x - A2.M3.x	H1: G2 requires less time for curation than G1 H1: G2 enable curation with less human intervention than G1
	A3.M4.X-∆ = A1.M4.x - A2.M4.x	Wilcoxon signed-rank test H1: The NLP system developed in G2 yields a higher precision than the NLP system from G1. H1: The NLP system developed in G2 yields a higher recall than the NLP system from G1.
A4	Difference in P1 and P2 (difference between the 2 patient arms)	Unpaired t-test (effect on training/experience) There is a difference in performance due to training/experience with the system : patients having used G1 are more/not more effective in G2 than patients who work with only one generation of the prototype (G1 or G2)
	Α4.Μ1-Δ = P1.Μ1-Δ - P2.Μ1-Δ	H1: G2 more usable than G1 (due to experience during G1)
	A4.M2.x-Δ = P1.M2.x-Δ - P2.M2.x-Δ A4.M3.x-Δ = P1.M3.x-Δ - P2.M3.x-Δ	H1: G2 requires less time for curation than G1 as patients are more experienced H1: There are less questions of the system unanswered during G2 than in G1 as the patient acquired experience in G1
	A4.M4	Not useful

Secondary Endpoint(s) Analysis

Description of measures	Test & meaning (per H1)
Breast Canc	er
Difference in data points 0 and 1 (i.e. difference between G0 and G1 across a sample of 15 patients) U0.TBCx- Δ = TBCx@SDP0 - TBCx@SDPA U0.EBCx- Δ = EBCx@SDP0 - EBCx@SDP1 U0.ACCx- Δ = ACCx@SDP0 - ACCx@SDP1	Unpaired t-test H1: G2 has more (or same) accuracy than G1 while keeping the same time saving and duration
	Descriptive Statistics around performance in G1 of the AIDAVA system (e.g. mean,)

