10.3.4 Data user/consumers spreadsheet: Breast Cancer Specialist and CVD clinicians

Breast Cancer

Form to be used by the Breast Cancer Specialist to enter time related to management of the BC registry

Breast Cancer Specialist - Data User Form - G0	
Site name:	 NEMC - Sihtasutus Põhja-Eesti Regionaalhaigla UM - Maastricht University MUG - Medizinische Universität Graz
Data User ID / pseudonym:	✓
To be computed for 45 patients across sites (15 patients in your own site + time to get info on 30 patients in t	he other 2 sites)
TBC1. Estimated time to compute the percentage of patients - across sites - treated with breast conserving therapy and whole breast radiotherapy that receive a boost to the tumour bed without AIDAVA (in min):	(example: 2 or 6 or)
TBC2. Estimated time to compute the number of patients - across sites - undergoing surgery and radiotherapy, without adjuvant chemotherapy: % of patients with time between surgery and radiotherapy > 8 weeks without AIDAVA (in min):	(example: 2 or 6 or)
TBC3. Estimated time to compute the number of patients - across sites - receiving radiotherapy: Percentage of patients receiving any nodal radiotherapy without AIDAVA (in min):	(example: 2 or 6 or)

This form is linked with a table that contains all the metrics manually entered in REDCap (as .csv-export) that are needed to evaluate the system from a BC specialist perspective.

Breast			G1				G2	
Cancer	BC1	BC2	BC3	Comments	BC1	BC2	BC3	Comments
NEMC								
MUG								
Maastro								
MEAN								
MEDIAN								

CVD specialist

Form to be used by the CVD specialist to enter the manually computed SMArt score and the time needed to compute this form manually

CVD Specialist - Data User Form - G1 & G2	
Generation of the prototype	 B O Generation 1 C Generation 2 reset
Site name:	 NEMC - Sihtasutus Põhja-Eesti Regionaalhaigla UM - Maastricht University MUG - Medizinische Universität Graz
Data User ID / pseudonym:	~
Patient ID / pseudonym:	
Date:	H Today Y-M-D
CVD1. SMART risk score computed by the physician(s) for the patient (from this site): U-prevent SMART risk score calculator	SMART risk score computed by CVD Specialist SMART risk score computed by another person Name of this other person
TCVD1. Time required for the treating physician to compute the SMART risk score (collect + analyze + enter data into a standalone web page calculator) in min:	(example: 10 or 20 or)

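### The breast cancer time endpoint is defined inconsistently between Protocol 3.2.1, 9.2 and the G0 form, and the form shown collects no effort value for the U0.EBCx contrast

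*Protocol*

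**What the plan says.** Section 3.2.1 (Breast Cancer Use case), Metric 1, defines the endpoint as "Time to have an answer to the 3 queries (BC1, BC2 and BC3) with information from the BC registry", across sites. It then qualifies this with "Note 1: should include time of the BC specialist and supporting team (spending most of the time". The only measurement listed there is TBCx, entered by the user for each query; EBCx does not appear in 3.2.1.

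Section 9.2 (Analysis Sets) lists two time variables at SDP0, the G0 data point. One is "EBCx: estimated total effort (person min, person hours or person days) for BC specialist and supporting local team to answer the queries". The other is "TBCx: estimated duration (min, hours or days) for the BC specialist to have an answer to the queries", with the clarification "Duration = time between the first request and the time the answer is provider".

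Section 10.3.4 shows the G0 form for the breast cancer specialist. It has three items, TBC1 to TBC3, one per query. The first begins "TBC1. Estimated time to compute the percentage of patients", and all three ask for minutes without AIDAVA. No item is labelled EBC or asks for person-time.

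Section 9.3 (Secondary Endpoint(s) Analysis) defines the U0 comparison of G0 with G1. It includes a difference in TBCx and a difference in effort, "EBCx@SDP0 - EBCx@SDP1".

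**The concern.** U0 is the only planned comparison of the breast cancer queries with current practice; the other contrast, U1, compares G1 with G2. The alternative hypothesis in 9.1 for this use case includes sparing the specialists and their supporting team the time they now spend. That is closest to EBCx, and EBCx is the variable with no field on the G0 form.

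The TBCx entries have a different problem. A specialist who follows Note 1 in 3.2.1 could enter the summed working time of everyone involved. One who follows 9.2 would enter the time from request to answer. The form does not settle which is wanted. The participant form in 10.3.2 has two breast cancer specialist slots per site, so a single different interpretation could weigh heavily in the G0 mean. A G0 value of one kind minus a G1 value of the other kind is not an interpretable time saving.

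**Working it through.** The protocol states no figure for this endpoint that could be recomputed, so the check sets the sections side by side.

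| Place | Variables named | Meaning | Unit | Patient base |
|---|---|---|---|---|
| 3.2.1, Metric 1 | TBCx only | Time to an answer, to include specialist and team time | Not stated | Across sites |
| 9.2, SDP0 | EBCx and TBCx | EBCx: total effort. TBCx: first request to answer | EBCx: person-minutes, -hours or -days. TBCx: minutes, hours or days | About 15 patients on site |
| 10.3.4, G0 form | TBC1 to TBC3 only | Time to compute; effort or elapsed not stated | Minutes | 45 across sites (15 own + 30 at the other two) |
| 9.3, U0 | EBCx and TBCx | As in 9.2 | Not stated | Sample of 15 patients |

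**Count of G0 inputs.** U0 needs TBCx and EBCx at SDP0 for three queries: 2 × 3 = 6 values per respondent. The form shown has 3 items, all TBC. So 6 − 3 = 3 values (EBC1, EBC2, EBC3) have no field.

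**Could the missing values come from elsewhere?** Section 9.2 says the measures come from REDCap forms or are computed. AIDAVA cannot compute the effort spent without AIDAVA, so a form is the only route the protocol gives. The list of REDCap forms in the main deliverable and the Schedule of Activities name one breast cancer data user form for G0, Form 12. On the page showing it, TBC1, TBC2 and TBC3 follow in order and then the closing sentence, with no gap or redaction mark.

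**Can the direction of a mix-up be predicted?** It cannot. As an illustration on assumed values, three people working 60 minutes each give an effort of 3 × 60 = 180 person-minutes. If they work in parallel with no waiting, elapsed time is 60 minutes, and 60 / 180 = 0.33. If the answer waits 5 days on other sites, elapsed time is 5 × 24 × 60 = 7,200 minutes, and 7,200 / 180 = 40. Elapsed time can therefore lie below or above effort. None of these inputs comes from the protocol, and the range is not an estimate of bias.

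**The G1 side.** After the G0 form, the text of 10.3.4 moves to a results table. The fields of Form 13, the breast cancer form for G1/G2, are not visible, so whether it collects EBCx, TBCx or both cannot be checked.

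**Neighbouring label.** The second term of the U0 difference in TBCx refers to a data point SDPA, which 9.2 does not define; SDP1 is presumably meant.

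**The case against.** The strongest reply is that the definitions are closer than they look. The core wording of Metric 1 in 3.2.1 is about when an answer is available, which nearly matches TBCx in 9.2; only Note 1 brings in team time. This stands. A reader might infer that 3.2.1 defines TBCx purely as labour and so flatly contradicts 9.2, but the text does not support that. Section 3.2.1 is mixed, and 9.2 later separates what it mixes.

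A reader might also infer that the G0 form asks for working time, because its example entries are small numbers. Those are placeholders, and the form's header includes the time to get information from the other two sites, which could cover waiting. The field is undefined and leans neither way.

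Three further inferences go too far:

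- It is not right that the plan has no effort baseline. Section 9.2 specifies EBCx at SDP0; what is missing is a field on the form shown.
- It is not established that G0 is effort while G1 is elapsed time, since the G1/G2 form cannot be seen.
- The saving would not be distorted by the ratio of the two quantities. U0 is a difference, and if the automatic queries bring the G1 time close to zero, the choice of G0 definition changes the size of the saving but hardly its sign.

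It can also be said that this is a secondary endpoint in a proof-of-concept study, and that details belong in the analysis plan. The first point limits the stakes. The second does not help, because an analysis plan cannot recover a value that was never collected.

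**Conclusion.** The point holds as an inconsistency that breaks one stated analysis and leaves another ambiguous. On the form shown, all three U0.EBCx contrasts lack a G0 value. The three U0.TBCx contrasts may rest on G0 entries that mix effort with elapsed time. No size or direction of error can be derived from the documents.

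This rests on two assumptions: that the displayed form is complete, and that no other instrument collects the effort spent at G0. Nothing is claimed about the content of the G1/G2 form. It should be corrected, but it concerns a secondary endpoint and does not touch the primary metrics.

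**What to change.** - Use the 9.2 definitions throughout: EBCx is total effort of specialist plus supporting team, and TBCx is elapsed time from first request to answer.
- In 3.2.1, list both variables under Metric 1 and attach Note 1 to EBCx.
- On the G0 form, ask two items per query: EBCx in summed person-minutes, and TBCx as elapsed time with its start and end points stated.
- Confirm that the G1/G2 breast cancer form collects the same pair in the same units.
- State one patient base for G0 and G1, reconciling about 15 on site (9.2) with 45 across sites (10.3.4), and correct the SDPA label in 9.3.

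The cost is three extra estimate fields per specialist on a REDCap form, plus wording changes in 3.2.1 and 9.3. Because the G0 values are estimates, the added burden is small. Whether EBCx or TBCx should carry the time part of the breast cancer hypothesis is the sponsor's choice; the correction does not depend on it.

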3.2.2 Cardiovascular Use case

Objective. The objective of the endpoints below is to demonstrate the value of having interoperable and reusable data in a standard format to generate valuable and high-quality information in clinical care, without additional burden to the treating physicians.

Objective	(Secondary) end point
Metric 1. Compare scoring time	Metric definition: Time to compute the SMART score (see
between AIDAVA and CVD	definition below)
expert	
	Measurement:

Objective	(Secondary) end point	
	TCVD. Time required for the treating physician to compute the SMART risk score (collect + analyse + enter data into a standalone web page calculator) - per estimate of user in dedicated entry form - compared to the time needed to calculate the same score by AIDAVA, automatically (G1 and G2)	
Metric 2: Compare scoring accuracy between AIDAVA and CVD expert	Metric definition: Accuracy of automatic calculation of the U-Prevent SMART risk score compared to cardiovascular expert-entered score calculation (% difference in the score output - per estimate of user in dedicated entry form) (G1 and G2)	
	 Measurement: CVD1. U-Prevent SMART score computed by treating physician (https://u-prevent.com/calculators/smartScore) CVD2. U-Prevent SMART score computed by AIDAVA 	

The SMART Risk Score [4] is a tool to estimate 10-year risk for recurrent vascular events in patients with manifest cardiovascular disease. The calculator is located at the U-Prevent site [5], a clinical decision support platform, for the application of risk prediction models in clinical practice; the calculator has been recreated and optimised by ORTEC for personalised cardiovascular risk management. The U-Prevent site is CE marked according to the Medical Devices Directives (MDD); marking for MDR compliance is in progress. The pilot site was built by UMC Utrecht. Using the calculators is free. The U-Prevent team develops extra services for premium users, optimization of data management, e.g. by FAIR and GDPR-compliant data exchange from electronic health records. Technical specification to compute Model A, the SMART Risk Score [6] can be found below.

Formulas	SNOMED / LOINC Code (available in PHKG)	Population ¹² value if missing
Recalibrated SMART risk score for	patients with CVD:	
10-year cardiovascular disease risk	: (%) = (1- 0.71840 exp[A + 1.933]) x 100%	
where A =		
-0.0349602236 x age in years	Compute from SNOMED: 184099003 Date of birth	Mandatory
+ 0.0005510715 x (age in	(observable entity)	
years)²		
+ 0.2876587433 [if male]	Answer is Y in case of presence of	Mandatory
	SNOMED: 248153007 Male (finding)	
+ 0.3455832714 [if current	A= last occurrence of smoker SNOMED: <<	Mandatory
smoker]	77176002 Smoker (finding)	(default = N)
	B = last occurrence of	
	Quit-Smoking (<< 160617001 Stopped smoking)	
	OR Ex-Smoker (<< 8392000 Non-smoker)	
	IF time of A is after B,	

¹² Numbers from Dutch population (baseline characteristics from the SMART study); it is valid for male/female and all ages. The same number can be used across the EU population.

Formulas	SNOMED / LOINC Code (available in PHKG)	Population ¹² value if missing
	THEN value is Y FLSE value is N	
+ 0.0018913154 * systolic blood pressure in mmHg	Take last value in PHKG ; SBP= LOINC: 8480-6	Mandatory
	(average value across a period of time)	
+ 0.3181706587 [if diabetic]	Answer is Y in case of presence of SNOMED: << 73211009 Diabetes mellitus (disorder) (and all children codes)	VAL = 17% * 0.223 (average)
+ 0.2947019539 [if history of coronary artery disease, of acute coronary syndrome, myocardial infarction or coronary revascularization]	 Answer is Y in case of presence of SNOMED: << 53741008 Coronary arteriosclerosis (disorder) (and all children codes) OR SNOMED: << 394659003 Acute coronary syndrome (disorder) (and all children codes) OR SNOMED: << 22298006 Myocardial infarction (disorder) (and all children codes) OR SNOMED: << 415070008 Percutaneous coronary intervention (procedure)>> (and all children codes) OR SNOMED: <<232717009 Coronary artery bypass grafting (procedure) >> (and all children codes) 	Mandatory (default = N)
+ 0.3483178604 [if history of cerebrovascular disease, TIA, brain infarction, amaurosis fugax, retina infarction or carotic surgery]	 Answer is Y in case of presence of SNOMED: << 230690007 Cerebrovascular accident (disorder) (and all children codes) OR SNOMED: << 266257000 Transient ischemic attack (disorder) (and all children codes) OR SNOMED: << 432504007 Cerebral infarction (disorder) (and all children codes) OR SNOMED: << 88032003 Amaurosis fugax (disorder) (and all children codes) OR SNOMED: << 175362007 Carotid and/or cerebral and/or subclavian artery operations (procedure) (and all children codes) 	Mandatory (default = N)
+ 0.3303566308 [if abdominal aortic aneurysm, history or presence of supra- or infrarenal aneurysm of the aorta > 3 cm, or aortic surgery]	 Answer is Y in case of presence of SNOMED: << 233985008 Abdominal aortic aneurysm (disorder) (and all children codes) OR SNOMED: << 67362008 Aortic aneurysm (disorder) (and all children codes) OR SNOMED: << 32907006 Operation on aorta (procedure) (and all children codes) 	Mandatory (default = N)
+ 0.2244665798 [if peripheral artery disease, history or presence of claudicatio intermittens, lowered ankle-arm index or surgical intervention (like angioplasty,	 Answer is Y in case of presence of SNOMED: << 840580004 Peripheral arterial disease (disorder) (and all children codes) OR SNOMED: << 63491006 Intermittent claudication (finding) (and all children codes) OR SNOMED: << 446841001 Ankle brachial 	Mandatory (default = N)

Formulas	SNOMED / LOINC Code (available in PHKG)	Population ¹² value if missing
stenting, endarterectomy, vascular bypass or amputation)]	 pressure index (observable entity) (and all children codes) OR SNOMED: << 387713003 Surgical procedure (procedure) (like <418285008 Angioplasty of blood vessel (procedure)> OR <233434005 Insertion of stent into vein (procedure)> OR <392031002 Endarterectomy (procedure)> OR <116360008 Arterial bypass graft (procedure)> (and all children codes) 	
 + 0.0476995851 x years since first diagnosis of vascular disease + 0.0016497342 x years since first diagnosis of vascular disease A2 	 years (YRS) = current year - Y1 (year of first diagnosis of any of the above 4 diagnosis groups) Y1 = smallest of A,B,C,D where A = year of first occurrence of coronary artery disease B = year of first occurrence of history of cerebrovascular disease C = year of first occurrence of abdominal aortic aneurysm D = year of first occurrence of peripheral artery disease years = YRS as above 	VAL= 1 year
+ 0.5403642493 x log(nonHDL)	 nonHDL = total-cholesterol - HDL-cholesterol WHERE total-cholesterol in mmol/L = Last value LOINC: 14647-2 OR if not available VAL = 4.9 mmol/l HDL-cholesterol in mmol/L = Last value LOINC : 14646-4 OR if not available VAL = 1.2 mmol/l 	For all lab value, if the unit of measurement is different in the ontology that the one in the formula transform with unit needed
+ 0.0396752081 * eGFR ² (in mL/min/1.73m ² + 0.0002186126 * eGFR ² (in mL/min/1.73m ²) + 0.1517601731 * log(High	Last value LOINC: 62238-1 If not available, derive from creat(SerumCreatine in micromol/l (LOINC = LP145994-2) (per paper Based on Heart. 2013 Jun;99(12):866-72 & Circulation. 2016 Nov 8;134(19):1419-1429 eGFR in mL/min per 1.73 m2 = If patient is male (SNOMED: 248153007) THEN = 32788 * creat ^(-1.154) * age ^(-0.203) ELSE 32788 * creat ^(-1.154) * age ^(-0.203) * 0.742 If the last value of LOINC: 30522-7 is above 15 then	VAL creatine = 92 micromol/l (to be transformed) VAL = 2.2mg/l =
Sensitivity-CRP in mg/dL)	use the previous value (up to the time the value is below 15). If there is no value below 15, then take default	22mg/dL

Formulas	SNOMED / LOINC Code (available in PHKG)	Population ¹² value if missing
+ 0.2107210313 * usingAnticoag	 Answer is Y in case of presence of one or more drugs of category Platelet aggregation inhibitors excl. Heparin (ATC = B01AC) OR A combination of One or more drugs of category Platelet aggregation inhibitors excl. Heparin (ATC = B01AC) + one or more drug of category Direct factor Xa inhibitors (ATC = B01AF) 	VAL = Y
	 Example: can be Ascal, aspirin or an other equivalent (AAS, carbasalate calcium) Dual antiplatelet therapy : Ascal / aspirin + a P2Y12 inhibitor Direct oral anticoagulants (DOAC) P2Y12 inhibitor Ascal / Aspirin + low dose direct working oral anticoagulation (DOAC) 	

In case of missing data, some parameters can use population average value as indicated in the last column. If a mandatory value is missing, the default value indicated in the last column will be used. Note: it is expected that birthdate, gender and systolic blood pressure will be available. The score will be computed by AIDAVA and by the treating (junior) physician. It will then be checked by the senior physician; in case of discrepancy between the score computed by AIDAVA and by the physicians, the senior physician will require explanations on how AIDAVA came to the different answers/codes needed to compute the score and decide the reason for discrepancy.

The senior physicians will be presented with a table with all the parameters used to compute the score (as displayed in the figure below) and be able to get information on how AIDAVA came to a certain value (which data source, which transformation).

The senior physician will then be able to decide on one of the following reasons for discrepancy. Health record incomplete: the information was not available in the medical record, while it should have been – and therefore AIDAVA could not identify the right value.

- Error in AIDAVA: the information is rightly included in the medical record, but AIDAVA did not include this information properly
- Error from physician: AIDAVA is right and the junior physician evaluation is not correct.

To assess the longitudinal aspects of AIDAVA, the SMART score will be calculated 2 times (after G1 and \pm 16 to 18 months later, at the end of G2 use year follow-up). The aim is to see if modifiable risk factors can be captured and risk can be calculated by AIDAVA automatically and reliably.

4. Study Design

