- Alternative hypothesis (H2 CVD): AIDAVA G1 provides an accurate SMART score (accuracy of 80%+) on patients, across sites, without any time spent by CVD specialists. G2 has similar or better results.

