11.1 Regulatory and Ethical Considerations

From an ethical point of view, the AIDAVA-curated data will NOT be presented to clinicians and patients as being reliable for final use, but as a research prototype output to be validated before use (if they choose to) in the care process or clinical research activities.

The partners intend, provided that this project demonstrates success, to obtain Medical Device Regulation certification so that the outputs can be accepted and used. This will only occur after the project.

- This study will be conducted in accordance with the protocol and with the following:
 - Consensus ethical principles derived from international guidelines including the Declaration of Helsinki and Council for International Organizations of Medical Sciences (CIOMS) international ethical guidelines
 - Applicable ICH Good Clinical Practice (GCP) guidelines
 - Applicable laws and regulations
- The protocol, protocol amendments, ICF, SIP will be submitted to an IRB/IEC by the investigator and reviewed and approved by the IRB/EC active in each of the study centres, before the study is initiated.
- Any amendments to the protocol will require IRB/EC approval before implementation of changes made to the study design, except for changes necessary to eliminate an immediate hazard to study participants.

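### The CVD time metric records no specialist time on the AIDAVA side, so the no-specialist-time clause of H2-CVD is assumed rather than measured

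*Protocol*

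**What the plan says.** Section 3.2.2 aims to show value in clinical care with no added load on the treating physician. Metric 1 defines the manual side as "Time required for the treating physician to compute the SMART risk score (collect + analyse + enter data"), with the entry made in an online calculator and the time estimated by the user. The AIDAVA side is "compared to the time needed to calculate the same score by AIDAVA, automatically (G1 and G2").

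The alternative hypothesis H2-CVD in 9.1 has two parts: an accuracy of at least 80%, and a score obtained "without any time spent by CVD specialists".

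Section 3.2.2 also has a senior physician check the computed scores. When the two disagree, "the senior physician will require explanations on how AIDAVA came to the different answers/codes needed to compute the score". That physician then names the cause of the difference. Section 11.1 says AIDAVA-curated data are presented "but as a research prototype output to be validated before use (if they choose to) in the care process"; the same holds for research.

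On data capture, the CVD form in 10.3.4 (REDCap Form 14) has one duration field: "TCVD1. Time required for the treating physician to compute the SMART risk score". The analysis set in 9.2 lists TCVD1.1 and TCVD1.2, the treating and senior physicians' times to compute the score. The patient monitoring forms in 10.3.2 ask only whether the score was viewed, yes or no.

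**The concern.** The two sides of the comparison have different boundaries. The physician is timed from gathering the data to having a score. AIDAVA is timed for the calculation alone. A specialist who uses AIDAVA's score has at least to open it, and may read through the inputs, and none of those minutes is recorded.

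What is at stake is the conclusion about physician burden. A version of AIDAVA whose score takes a specialist some time to read and accept would show the same time result as one that needs no attention. Minutes that are not noted when they are spent cannot be recovered reliably afterwards, so this has to be settled in the endpoint definition and the form.

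**Working it through.** The protocol states no expected time for either route, so there is no figure to reproduce. The check traces specialist time through the document and then illustrates the size.

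**Where specialist time with AIDAVA could be recorded**

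- 3.2.2, Metric 1: manual effort against automatic calculation. No review time.
- 9.2, CVD rows: TCVD1.1 and TCVD1.2 are times to compute. The senior physician's TCVD1.2 is also time to compute, so it does not fill the gap.
- 10.3.2, monitoring forms: viewing is a yes/no item without a duration.
- 10.3.4, Form 14: manual computing time only. The reporting table under it has a TCVD2 column with no matching field on the form. Even if that column means AIDAVA's time, it would not hold review time.
- 4.4.2, Week 1 Day 5: the research associate is to document the result and time of the score calculation, but the monitoring form shown has no field for it, and calculation time is not review time.
- 9.3: TCVD is compared between G1 and G2 by a paired t-test. No AIDAVA-versus-physician test is listed.

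**Contrast within the protocol.** For breast cancer, Metric 1 in 3.2.1 is to include the time of the specialist and the supporting team. Section 9.2 carries a total-effort variable (EBCx) beside the duration (TBCx) for G0, G1 and G2. The CVD use case has no counterpart to EBCx.

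**Illustration of size.** Inputs: manual time T_m = 10 or 20 min, the example entries printed beside the field on Form 14 and not expected values; computing time T_a = 0 to 1 min (assumed); specialist review T_r = 2, 5 or 10 min (assumed). Adjudication of discrepancies is left out.

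Saving as Metric 1 is defined = T_m − T_a:

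- T_m = 10: 10 − 1 = 9 to 10 − 0 = 10 min (90% to 100%)
- T_m = 20: 20 − 1 = 19 to 20 − 0 = 20 min (95% to 100%)

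Specialist time saved once review is counted = T_m − T_r:

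| T_r (min) | T_m = 10 | T_m = 20 |
|---|---|---|
| 2 | 8 min (80%) | 18 min (90%) |
| 5 | 5 min (50%) | 15 min (75%) |
| 10 | 0 min (0%) | 10 min (50%) |

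Adding 1 min of computing lowers each entry by 1 min, so the range becomes −1 to 17 min. In specialist time the break-even is T_r = T_m, that is 10 or 20 min of review.

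**The case against.** Several stronger readings are tempting, and the documents do not support them.

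- A reader might infer that H2-CVD cannot be refuted, or that AIDAVA wins by definition. H2-CVD is a joint claim, and the accuracy part can fail. A version with many discrepancies would show up in Metric 2, in the accuracy variables of 9.2 and in the recorded reasons for discrepancy. Section 9.3 also plans no test that would declare AIDAVA the winner over the physician.
- A reader might infer that the senior physician's discrepancy work is a cost of using AIDAVA. It arises because the study produces two scores for the same patient, and one listed outcome is that the junior physician was wrong. It is largely study adjudication. Routine use would have no second score to reconcile.
- A reader might infer that 11.1 makes validation compulsory. The sentence leaves use to the clinician's choice, and the protocol bars the prototype from clinical decision making. It supports the idea of a review step but does not lay down a workflow.
- A reader might infer that patient and curator time is lost. It is recorded under primary Metric 2. Leaving it out of a physician-burden metric is coherent, the more so because one curation serves several outputs.
- Review time measured after the same physician has scored the patient by hand is contaminated by knowing the answer. This is a fair limit on the remedy and shapes how the field should be filled in.

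What remains is the time clause. It speaks of specialist time, and specialist time with AIDAVA is not collected.

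**Conclusion.** The point holds in a limited form. The comparison in 3.2.2 sets full manual effort against computing time, and nothing shown captures the minutes a specialist spends opening or reviewing AIDAVA's score. The time clause of H2-CVD and the aim of no added physician burden are therefore taken for granted, not tested. The accuracy clause is unaffected.

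The size is unknown. The 0% to 90% range in specialist time rests wholly on assumed review times and on form placeholders. It shows only that the answer depends on a quantity the study does not record. This is a secondary endpoint in a proof-of-concept study, so the consequence is a conclusion about physician burden that the data cannot carry, and not a threat to the primary comparison.

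**What to change.** - Add to Form 14 the minutes a CVD specialist spends opening and reviewing AIDAVA's score. Where feasible, record them before the reviewer sees the manual score.
- Record the minutes spent adjudicating discrepancies under 3.2.2 separately, and do not charge them to AIDAVA.
- Report specialist review time per AIDAVA score against manual scoring time for the same patient.
- Reword the time clause of H2-CVD as less specialist time than manual scoring.
- Patient and curator minutes from Metric 2 may be shown alongside but should not be added to TCVD.
- If the field is not added, limit the claim in 3.2.2 and 9.1 to computation time.

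The cost is one review-time field, a separate entry for adjudication minutes if these are kept, and a few changed sentences. The reported saving may turn out less favourable.
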